11.5. Reporting to the EMA42
12. REFERENCES43

LIST OF TABLES

Table 0-1: Registry Flowchart6
Table 2-1: Opportunistic Infections11

LIST OF ABBREVIATIONS

ADR	adverse drug reaction
AE	adverse event
CHMP	Committee for Medicinal Products for Human Use
CRF	case report form
DMARDs	disease-modifying anti-rheumatic drugs
DSU	Drug Safety Unit
EC	Endpoint Committee
EDC	electronic data capture
EIU	exposure in-utero
EMA	European Medicines Agency
EU	European Union
FDA	US Food and Drug Administration
GPP	Good Pharmacoepidemiology Practices
ICF	informed consent form
ICH	International Committee on Harmonisation
IEC	independent ethics committee
ISPE	International Society for Pharmacoepidemiology
JC virus	John Cunningham virus
JIA	juvenile idiopathic arthritis
MedDRA	Medical Dictionary for Regulatory Activities
NICE	National Institute for Health and Clinical Excellence
NRP	national responsible person
PASS	post-authorisation safety study
PSUR	periodic safety update report
PUVA	psoralen ultraviolet A phototherapy
RA	rheumatoid arthritis
RMF	registry master file
RP	registry physician
RSF	registry site file
SAE	serious adverse event
SAP	statistical analysis plan
SIR	standardized incidence ratio
SSC	Scientific Steering Committee
TB	tuberculosis
TNF	tumour necrosis factor
UV	ultraviolet

Table 0-1: Registry Flowchart

Study Interval	Data Collected		
	Enrolment	Year 1 – Year 2	Year 3 – Year 5 ^a
	Baseline	Every 3 months (± 4 weeks)	Every 6 months (± 4 weeks)
Visit ID	1	2 – 8	9 – 12
Informed consent/assent	X		
Patient/legal representative contact information	X	X	X
Demographics	X		
Medical history	X		
Co-morbidities	X	X	X
Psoriasis history (including date of diagnosis, severity assessment, previous treatments)	X		
Etanercept exposure	X ^b	X	X
Treatment discontinuation		X	X
Other systemic psoriatic treatments ^b	X	X	X
Prior medications	X		
Concomitant medications	X	X	X
Serious and pre-specified opportunistic infections ^c	X ^b	X	X
Malignancies ^c	X	X	X
Other adverse events ^c		X	X
Registry discontinuation ^d	0	-----	X

- Patients enrolled after September 2013 may be followed for less than 5 years (i.e., until overall study completion in 2018)
- For patients being treated with etanercept prior to enrolment, details regarding etanercept dose and regimen, other systemic treatments, and serious and pre-specified opportunistic infections occurring since the first etanercept dose but before enrolment will be collected via retrospective medical record abstraction.

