4.2. Inclusion Criteria

To be eligible for registry enrolment, patients must meet all of the following criteria:

- Age ≤ 17 years at time of administration of the first dose of etanercept
- Diagnosis of plaque psoriasis by a dermatologist
- Prior to enrolment, a clinical decision has been made to prescribe etanercept for the treatment of psoriasis
- Newly prescribed with initial etanercept or actively being treated with etanercept, regardless of length of treatment prior to study enrolment
- Capable and willing to provide paediatric assent, or written informed consent when applicable, and
- Parent(s)/legal representative of patient is capable and willing to provide written informed consent

- Evidence of a personally signed and dated informed consent document indicating that the patient (or a legally acceptable representative) has been informed of all pertinent aspects of the study must exist.

Please note: Currently etanercept is approved for the treatment of severe plaque psoriasis in children and adolescents from the age of 6 years who are inadequately controlled by, or are intolerant to, other systemic therapies or phototherapies. The registry protocol will not encourage use of etanercept at younger ages. However if a doctor, in collaboration with the child's parents, makes the independent clinical decision to prescribe etanercept to a child less than 6 years of age for severe plaque psoriasis, that child may be included in the registry.

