4.3. Exclusion Criteria

Patients are not eligible for this registry if they meet any of the following criteria:

- Prior therapy with any biologic agent other than etanercept
- History of malignancy
- Unlikely to complete a minimum of two years of follow-up, based on physician's judgment (i.e., social issues, family illness, plan to move out of area, living too far from the physician's office to adhere to standard of care visit schedule)
- Participation in any study involving any experimental drug or device within the last 30 days or 5 elimination half-lives, whichever is greater
- Other severe acute or chronic medical or psychiatric condition or laboratory abnormality that may increase the risk associated with study participation or may interfere with the interpretation of study results and, in the judgment of the investigator, would make the patient inappropriate for entry into this study.

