6.2.1. Baseline Visit

During the enrolment visit, the site will be instructed to obtain additional information regarding the patient, including secondary contact information and contact information for the patient's primary health care provider.

The following information will be collected:

1. Date of informed consent(s)/assent
2. Patient/legal representative contact information, including secondary contacts and primary health care provider details, if different than RP
3. Demography [age, gender, weight, race/ethnicity (where allowed by local regulation)]
4. Medical history/co-morbid medical conditions
5. Plaque psoriasis history
 - a. Physician's global subjective assessment of disease severity (four-point scale)
 - b. Prior treatments or therapies, including topical agents and immunosuppressive therapies and the patient's response to each.
6. Etanercept Treatment
 - a. Initial prescribed etanercept treatment regimen
 - b. Date of first dose
7. Concomitant medications, including immunosuppressants
8. Retrospective medical record abstraction for patients with historical treatment with etanercept will also include:
 - a. Etanercept dosing history
 - b. Use of additional systemic therapies since starting etanercept
 - c. Occurrence of serious and/or pre-specified opportunistic infections and SAEs

Note: Due to the significance of the AEs of interest (serious and opportunistic infections and malignancies), it is considered highly likely that these events, if they occurred, would be documented in the medical record of the prescribing RP. Retrospective data for other SAEs overall, however, may not be consistently recorded; therefore, all retrospective SAEs will be collected but analysed separately.

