7.1. General considerations

All AE verbatim terms will be recorded and coded using MedDRA. Statistical analysis of all data will be performed using SAS[®] statistical software (SAS Institute, Cary, NC, USA).

Frequencies of defined outcomes will be described. If possible, analyses will also be performed using the different etanercept treatment status (i.e., current/recent versus past treatment) and etanercept cumulative dose exposure groups.

Analysis of the characteristics of patients enrolled in the registry and of those who did not consent to participate (to the extent feasible) will help evaluate whether there are any differences between registry enrollees and non-respondents, i.e., generalizability.

Primary analyses will be limited to prospective data, i.e., events reported during participation in the registry. Serious and pre-specified opportunistic infections and malignancies reported as part of retrospective data collection will be summarized separately.

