## **PURPOSE SAP**

**Protocol # B1801035**

Any patient who receives at least one dose of etanercept will be included in the evaluation for safety. The primary focus of this Registry is safety; however, to the extent possible effectiveness (or lack of effectiveness) will be inferred from patterns of treatment and re-treatment. In addition, the change of severity of plaque psoriasis as a measure of effectiveness will also be assessed, if these data are available among the majority of patients.

Primary analyses will be limited to prospective data, i.e., events reported during participation in the registry. Serious and pre-specified opportunistic infections and malignancies reported as part of retrospective data collection will be included in a summary of medical history and co-morbid conditions.

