### 7.1 Summary of baseline characteristics and demography

For enrolled patients, line listings for all baseline characteristics (including medical history) and demography data will be generated.

The following tabular summaries will be generated:

- Demography (age at enrollment, gender, race/ethnicity)
- Plaque psoriasis status (duration of disease, baseline severity, presence of psoriatic arthritis, age at diagnosis of plaque psoriasis)
- Previous/current plaque psoriasis therapies (proportion of patients with previous/current use of topical steroids, methotrexate, cyclophosphamide, etc)

Demography summary will also be generated by gender as per basic result disclosure (Pfizer standard).

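### The SAP does not guarantee the separate presentation that the protocol promised for infections and SAEs arising between the first etanercept dose and enrolment

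*SAP*

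**What the plan says.** Patients may enter while "actively being treated with etanercept, regardless of length of treatment prior to study enrolment" (Protocol 4.2). For them, a footnote to the registry flowchart (Protocol Table 0-1) says that "serious and pre-specified opportunistic infections occurring since the first etanercept dose but before enrolment will be collected via retrospective medical record abstraction". Item 8c of the baseline list in Protocol 6.2.1 adds SAEs to that abstraction.

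The protocol then gives two reporting rules:

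- Infections and malignancies (Protocol 7.1): "Serious and pre-specified opportunistic infections and malignancies reported as part of retrospective data collection will be summarized separately".
- SAEs (Protocol 6.2.1): "all retrospective SAEs will be collected but analysed separately".

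SAP section 4 keeps the protocol's restriction, "Primary analyses will be limited to prospective data, i.e., events reported during participation in the registry", but changes the rule that follows it: the infections and "malignancies reported as part of retrospective data collection will be included in a summary of medical history and co-morbid conditions". The SAP output that carries medical history is described in SAP 7.1: "line listings for all baseline characteristics (including medical history) and demography data will be generated". Medical history is not among the tabular summaries listed there.

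**The concern.** Medical history normally means what the patient brought to treatment. SAP 5.4 uses it in that sense, listing medical history and co-morbid conditions among the baseline covariates. The abstracted infections are a different kind of data: by definition they arose after the first etanercept dose. Putting them in the same summary turns post-exposure safety events into background and mixes them with conditions that may be years older than the drug exposure.

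The registry's first objective is to describe infection risk with current or recent etanercept, and the recruitment target is 60 to 80 patients, so each serious infection carries information. Protocol 7.6 also warns that already-treated entrants may under-represent patients who did not tolerate the drug. A clear account of what happened to them between first dose and enrolment would help a reader judge that. At stake is whether these events are visible as a group, which is what the protocol undertook to provide.

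**Working it through.** No arithmetic is needed to establish the conflict. The check sets the sections side by side.

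**1. What the events are.** Table 0-1 fixes the window for infections: from first etanercept dose to enrolment. Protocol 6.2.1 lists their abstraction (item 8c) apart from medical history and comorbidities (item 4), so the protocol itself does not treat them as medical history.

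**2. What the protocol requires and what the SAP does.**

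| Event type, first dose to enrolment | Protocol | SAP |
|---|---|---|
| Serious and opportunistic infections | Separate summary (7.1) | Medical-history summary (section 4); 7.1 names only a line listing |
| Other SAEs | Separate analysis (6.2.1) | No rule in section 4; no separate analysis in 7.5 or 7.6 |
| Malignancies | Separate summary (7.1) | Medical-history summary (section 4) |

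The infection row is a change of rule. The SAE row is an omission. The malignancy row has almost no content, because "History of malignancy" is an exclusion (Protocol 4.3), item 8c does not list malignancies, and the malignancy row of Table 0-1 does not carry the retrospective-abstraction footnote.

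**3. Whether another SAP output fills the gap.** There are three candidates. SAP 7.3 lists and tabulates all serious and opportunistic infections. SAP 7.5 does the same for all SAEs. SAP 5.2.4 counts an event as treatment-emergent if its onset is on or after the first etanercept administration reported in the study. Each can be read in two ways:

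- *Pre-enrolment events are included.* They then enter the same tables and incidence rates as prospective events. That conflicts with the restriction to prospective data and still does not show them apart. Neither listing names the enrolment date among its fields.
- *Pre-enrolment events are excluded.* The medical-history output is then the only place that the SAP names for the infections, and retrospective SAEs have no named place.

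Neither reading delivers the presentation in Protocol 7.1 and 6.2.1.

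**4. Whether the enrolment-type split fills the gap.** SAP 6.5 classes patients as prospective if they started etanercept within 30 days before enrolment or later, and as retrospective otherwise. The SAP document history mentions a retrospective-patients column in some tables. Both classify patients, not events. A retrospective patient contributes events both before and after enrolment, and a prospective patient can have up to 30 days of exposure before it.

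**5. A linked point on person-time.** SAP 6.6 defines time at risk for infections and other SAEs as the sum over treatment periods of (last dose − first dose + 1 + 28)/365.25, with no stated start at enrolment. Let E be the prospective events, T_post the exposure time after enrolment and T_pre the exposure time before it. If pre-enrolment events are left out but pre-enrolment time is kept, the rate becomes E/(T_post + T_pre) instead of E/T_post, which is lower by the factor T_post/(T_post + T_pre). The SAP does not say that T_pre is included, but nothing excludes it. T_pre cannot be calculated from the documents.

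**The case against.** The best defence is that in Protocol 7.1 the word for separate follows directly on the restriction of primary analyses to prospective data. It can mean no more than separate from the prospective analysis, and a medical-history summary satisfies that. This has force: the protocol does not expressly require separation from medical history. It does not remove the point, because the protocol collects these events as a distinct post-dose item, and the requirement for retrospective SAEs is not met on either reading.

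Four stronger readings are tempting, and the documents do not support them.

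- *These infections will appear only as medical history, and readers will be unable to recognise them.* SAP 7.3, 7.5 and 5.2.4 leave a route open, and the table and listing shells are not part of the documents. The supportable statement is that the SAP does not guarantee a separate presentation.
- *Malignancies on etanercept are being reclassified as comorbidity.* A patient with a malignancy before enrolment should not be in the registry.
- *The primary result is distorted.* Both documents keep retrospective events out of the primary analysis, so the intended event counts stand. The denominator question in step 5 is an ambiguity, not a demonstrated bias.
- *A particular number of infections is affected.* The documents give neither the number of already-treated patients nor their prior exposure. A rate could be borrowed from the Phase 3 study described in Protocol 1.1: 3 severe infections over 211 × 24/52.18 = 97 patient-years, or 3.1 per 100. Assuming 14 patients with 24 weeks of prior use (6.4 patient-years) gives about 0.2 events. Assuming 35 patients with 3 years (105 patient-years) gives about 3.2. The answer is set by the assumptions, and one of the three infections is a gastroenteritis-associated dehydration. These figures are not relied on.

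**Conclusion.** The point holds in a limited form. For serious and pre-specified opportunistic infections, SAP section 4 replaces a separate summary with a place in medical history. For retrospective SAEs, the SAP names no analysis at all. Other SAP outputs may capture some of these events, but only on a reading that conflicts with section 4, so the protocol's commitment is not secured.

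Its size cannot be stated as a number of events. It depends on how many patients were already treated, which the protocol expects to be few. What would be lost is visibility of post-dose safety events, not the validity of the intended prospective counts. The conclusion rests on the SAP text as given; shells that already show these events apart would reduce the point to a wording correction. It should be put right because the protocol already requires the output and the data are already collected.

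**What to change.** In SAP section 4, replace the sentence on retrospective events with:

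> Serious infections, pre-specified opportunistic infections and other SAEs (and any malignancy) with onset from the first etanercept dose to the day before enrolment will be presented in a separate table and listing (patients, events, time from first dose, exposure status at onset where dates allow), and excluded from the primary prospective rates.

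Then state that the prospective summaries in SAP 7.3 and 7.5, and those based on the treatment-emergent definition in 5.2.4, count only events from enrolment onward, and that the person-time in those rates likewise starts no earlier than enrolment.

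Leave all other pre-enrolment comorbidities in the medical-history summary. Limiting that summary to conditions before the first dose would leave non-serious conditions arising between first dose and enrolment in no output.

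The cost is SAP wording plus one table and one listing. No new data are needed, and the intended primary analysis does not change.

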## **5. Variables Used for Analysis**

### **5.1 Data Sources**

Data will be collected from treating physicians, who will provide information on current medications and status of the Registry patients at enrolment and at each suggested follow-up assessment.

Following enrolment in the registry, the physician will also provide information by retrieving medical record information at his/her own institution and other health care settings, as appropriate. Data will be collected and recorded directly from the patient or their parent/guardian only if the patient has been lost to follow-up by the physician. If any of the outcomes of interest are reported directly by patients or their parents/guardians, additional attempts to collect supporting information from treating physicians will be made. In order to provide complete narratives for interim and final study reports, for any reported malignancies, any additional information provided via NIS SAE Form AEM01 and other follow-up reports to Pfizer's drug safety department or the Endpoint Adjudication Panel will be used to augment the data collected in the CRF.

Baseline data are expected to be recorded at the time of enrolment to this registry. Follow-up data are to be collected every 3 months ( $\pm$  4 weeks) during the first 2 years, and every 6 months ( $\pm$  4 weeks) during Year 3 through Year 5 of participation, either at the time of routine clinical visits, or alternatively via telephone interview.

### **5.2 Definition and measurement of outcomes of interest**

#### **5.2.1 Serious and opportunistic infections**

Analyses will include all episodes of serious infection experienced by a single individual.

**Serious infections** are defined as any infections that:

- Are life-threatening or resulting in disability
- Require intravenous antibiotic treatment

## PURPOSE SAP

Protocol # B1801035

- Require hospitalization

Serious infections are also further classified as nosocomial or not nosocomial/unknown.

Serious infections are characterized by the physician's open text report of infection site (i.e., bodily location), open text report of pathogen, date of diagnosis, date of resolution (or ongoing) and most recent dose of etanercept prior to diagnosis. If date of most recent dose is not known, whether the dose was within 28 days prior to diagnosis is requested (refer to [Section 5.3.1](#) for further details regarding establishing exposure at the time of infection diagnoses).

**Opportunistic infections** of interest include the following protocol-specified infections and pathogens (see table below):

All infections, including the designation as serious, opportunistic or nosocomial, will be reviewed by the Registry's Endpoint Adjudication Panel prior to inclusion in any analyses.

Bacterial	Fungal	Protozoan	Viral
Salmonella bacteraemia	Aspergillus sp. (Aspergillosis)	Cryptosporidiosis	Cytomegalovirus
Campylobacteriosis	Invasive Candida albicans	Isosporiasis	
Shigellosis	Coccidioidomycosis	Microsporidiosis	JC Virus (progressive multifocal leukoencephalopathy)
Mycobacterium tuberculosis	Cryptococcosis		Disseminated or central nervous system herpes zoster
Mycobacterium avium	Histoplasmosis	Acanthamoebiasis	Kaposi's sarcoma (herpesvirus 8)
Mycobacterium kansasii	Blastomycosis	Toxoplasmosis	BK virus
Syphilis/neurosyphilis	Paracoccidioidomycosis	Trypanosomiasis (Chagas disease)	
Pseudomonas aeruginosa	Sporotrichosis	Leishmaniasis	
Acinetobacter baumannii	Penicilliosis		
Listeriosis	Zygomycosis		
Nocardiosis	Pneumocystosis		
Legionellosis			
Actinomycosis			
Bartonellosis			

### 5.2.2 Malignancies

The following malignancies are reported as part of the Registry:

Version 5.0 dated 12Feb2019

## **PURPOSE SAP**

### **Protocol # B1801035**

- Solid malignant tumors
- Non-melanoma skin cancers
- Malignant tumors of hematopoietic and lymphoid tissues
- Carcinomas in-situ

The malignancy type is specified by open text. In order to meet the case definition for malignancy, a pathology report or a physician's notation of specific tumor histology will be required. All malignancies will be evaluated and coded by the Registry's Endpoint Adjudication Panel prior to inclusion in any analyses.

#### **5.2.3 Other adverse events**

All other Serious Adverse Events (SAEs) and non-serious Adverse Events (AEs) will be collected and coded using Medical Dictionary for Regulatory Activities (MedDRA). All SAEs will be reviewed by the Endpoint Adjudication Panel prior to inclusion in any analyses. As part of the data collection for the Registry, physicians are also asked whether pregnancy exposure, lactation exposure, medication error (overdose, or inadvertent or accidental exposure) have occurred. These are to be reported for the purposes of meeting regulatory reporting requirements but are not part of the objectives of the Registry and are not included as part of any analyses.

#### **5.2.4 Treatment emergent adverse events**

Treatment emergent adverse events will be defined as events having onset date greater or equal to the first administration of Enbrel reported in the study. All events with missing start date will also be considered as treatment emergent.

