### **7.5 *Other serious adverse events associated with exposure***

A patient listing of all SAEs will be generated, including verbatim term and MedDRA SOC and PT, onset date, total cumulative exposure at time of onset, date of last dose of etanercept prior to onset, date of first dose of etanercept and calculated interval between last dose and onset in days [if precision of event dates allow, otherwise use response to question whether within 28 days (yes, no, unknown)].

The following summaries will also be presented:

- Number of unique patients, total number of events, and incidence rate of all reported SAEs (by MedDRA SOC and PT)
  - Including serious and opportunistic infections and excluding malignancies
  - Excluding serious and opportunistic infections and malignancies
  - By treatment period (initial 24 weeks/ post 24 weeks/all follow-up)

Summary of SAE distribution [mean # of events reported per patient (SD), median, range]

Summary of serious TEAE will also be provided as per basic results disclosure (Pfizer standard).

The events described will be identified based on serious yes/no variable reported as Yes and onset date greater or equal to the first administration of Enbrel reported in the study. Serious events with missing onset date will be also included.

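### The SAP's treatment-emergent rule has no enrolment bound and counts all undated events, so it can admit retrospective SAEs that the protocol says are analysed separately

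*SAP*

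**What the plan says.** SAP 5.2.4 defines treatment-emergent adverse events (TEAEs) as "events having onset date greater or equal to the first administration of Enbrel reported in the study". It then adds: "All events with missing start date will also be considered as treatment emergent". SAP 7.5 builds the serious TEAE table on the same rule, "onset date greater or equal to the first administration of Enbrel reported in the study", and closes with "Serious events with missing onset date will be also included". Neither section refers to the enrolment or consent date. The opening of SAP section 7 makes everyone in the registry the default population for tables. Sections 7.5 and 7.6 neither restrict the TEAE tables by enrolment type nor stratify them by it.

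Protocol 4.2 admits children who are "actively being treated with etanercept, regardless of length of treatment prior to study enrolment". Under Protocol 6.2.1 the baseline visit records "Date of first dose" for every patient. For those already treated, earlier dosing and earlier infections and SAEs are also abstracted from the chart. The note in that section expects infections and malignancies to be well documented there but other SAEs to be recorded unevenly, and therefore says "all retrospective SAEs will be collected but analysed separately".

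SAP section 4 states: "Primary analyses will be limited to prospective data, i.e., events reported during participation in the registry". Its next sentence moves retrospectively collected serious and opportunistic infections and malignancies into the medical history summary. Other retrospective SAEs are not mentioned.

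**The concern.** For a child already on etanercept, the earliest dose in the registry data lies before enrolment. A rule that starts at that dose, with no enrolment bound, lets an SAE from the time before enrolment qualify as treatment emergent. The rule for undated events goes further and admits such an event wherever the start is placed.

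At stake is whether the TEAE tables, several of which feed basic results disclosure, stay free of events that the protocol itself regards as incompletely recorded. Protocol 7.6 adds that children still on treatment at enrolment may be those who tolerate the drug, which could bias their estimated risk downwards. Mixing the two sources blurs a distinction that the protocol drew on purpose. Because the start of the window is ambiguous, two programmers could also produce different disclosure tables from the same data.

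**Working it through.** No figure in the plan needs reproducing. The check applies the rule to a test case, looks for any other text that would remove the events, and then sizes the effect.

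**1. Test case (assumed).** First dose 12 months before enrolment, SAE 3 months before enrolment, enrolment at month 0.

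| SAE from chart abstraction | Start = earliest dose recorded (month −12) | Start = first dose during participation (month 0 or later) |
|---|---|---|
| Dated, month −3 | −3 is after −12: a TEAE | −3 is before 0: not a TEAE |
| No start date | a TEAE | a TEAE |

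The dated event depends on the reading. The undated event does not.

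**2. Would other text remove these events?**
- The limit to prospective data in SAP section 4 and Protocol 7.1 applies to primary analyses. The TEAE tables are added in SAP 7.5 and 7.6 as sponsor-standard and disclosure outputs and are not labelled primary.
- The redirection to medical history in SAP section 4 covers infections and malignancies only.
- Enrolment type is a planned subgroup in SAP 6.5 only where a section calls for it, and 7.5 and 7.6 do not. It would not be a substitute in any case: the prospective type allows a first dose up to 30 days before enrolment.

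**3. Where is the separate analysis?** SAP 7.5 lists no retrospective SAE table. SAP 9.3 says that the final report covers the analyses described in the SAP. The commitment in Protocol 6.2.1 therefore has no analysis behind it in the SAP text for SAEs other than infections and malignancies.

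**4. Size per affected patient.** The recruitment target in Protocol section 3 and SAP section 4 is 60 to 80. One extra patient with an event adds 1/80 = 1.25 to 1/60 = 1.67 percentage points.

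**5. Size in events (assumed inputs).** Events = patients already treated × years of prior exposure × SAE rate. The documents give none of the three. Take 1 to 2 years and 2 to 5 SAEs per 100 patient-years.
- 5 patients: 5 × 1 × 0.02 = 0.1 to 5 × 2 × 0.05 = 0.5 events.
- 20 to 30 patients: 20 × 1 × 0.02 = 0.4 to 30 × 2 × 0.05 = 3.0 events.

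The second case means 20/80 = 25% to 30/60 = 50% of the target, which is hard to square with Protocol 6.2, where few such patients are anticipated. Both ranges use a rate for all SAEs, including those that SAP section 4 already redirects, so they lean high for the remaining SAEs.

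**The case against.** The case on the other side has four parts.

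- **The phrase can be read the other way.** It may mean the first dose given during participation, and then dated events from before enrolment stay out. This stands, and it is why entry of dated events can only be stated conditionally.
- **Retrospective SAEs may never reach the adverse event data.** Protocol sections 9 and 9.2 start adverse event recording at enrolment. The flowchart (Table 0-1) has no baseline mark for other adverse events, and its footnote on retrospective abstraction names infections as the only events. Only Protocol 6.2.1 lists SAEs. This also stands as an uncertainty: the case report form is not available, and the two protocol passages disagree.
- **The table shells may handle it.** The SAP's document history mentions a column for retrospective patients in some table series. That is possible, but the shells are not available, and a column by patient type does not separate events by onset.
- **The prospective limit may already settle it.** A reader might infer the opposite, that this limit fails even for primary analyses because charts are abstracted after consent and so during participation. The documents do not support that inference. The sentence that follows the limit, in both the SAP and Protocol 7.1, treats retrospectively collected data as a separate category, so its meaning is clear enough. What remains true is that the limit is confined to primary analyses.

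A reader might also infer that the serious share of events must be inflated, since only serious events are abstracted. That overlooks the redirection of infections and malignancies to medical history, and the doubt over whether other SAEs arrive at all.

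**Conclusion.** The point holds in a limited form. The undated-event rule conflicts with Protocol 6.2.1 on either reading, and the dated rule conflicts with it on its natural reading, the earliest dose recorded. Both conclusions assume that retrospective SAEs are entered in the data from which the TEAE tables are drawn. Separately from that assumption, the SAP text has no analysis of retrospective SAEs other than infections and malignancies.

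A reader might conclude that retrospective SAEs will certainly enter the TEAE tables. The documents do not establish that. The number of patients affected is not stated and the effect is probably small: 0.1 to 0.5 events if five children are affected, under the assumed exposure and rates. The change is worth making because it is cheap, removes a contradiction between the two documents, and concerns disclosed tables. It does not call the registry's primary analyses into question.

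**What to change.** - In SAP 5.2.4 and 7.5, require onset on or after the later of the first etanercept dose and enrolment. This matches the protocol's adverse event reporting period, which begins once consent has been given and at least one dose received.
- In the same sections, exclude retrospectively abstracted events from the TEAE and serious TEAE tables, including those without a date. Keep the missing-date rule only for events reported prospectively.
- Add one table of retrospective SAEs, including the undated ones, to carry out Protocol 6.2.1.
- Reconcile the protocol flowchart with Protocol 6.2.1 on whether SAEs other than infections are abstracted retrospectively.

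The definition of prospective data in SAP section 4 can stay as it is. The cost is a few sentences and one extra table. First-dose and enrolment dates are already collected, and the SAP's SAE listing already uses onset date. A count of abstracted SAEs, dated and undated, would show at once whether any table changes.
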